Assuming a minimum of 4 screws per patient, the estimated probability of at least one non-clinically acceptable screw is 12% in the robotic group and 25% in the navigated and free hand group.

Using a two-sided alpha of 0.05, 80% power, and a 1:6 group ratio, the required sample size is 71 patients in the robotic-assisted surgery group and 426 patients in the non-robotic-assisted surgery group, for a total of 497 patients. We added patients to 75 in the robotic-assisted surgery group, for a total of 501 patients, to be able to include an equal number of patients from Örebro, Umeå and Uppsala. This estimate is conservative, as most patients are expected to receive more than 4 screws, which would increase the likelihood of detecting placement differences.

The primary analysis will use either mixed-effects logistic regression or logistic regression with cluster-robust standard errors to account for intra-patient correlation of screw outcomes.

A secondary analysis of robot-assisted surgeries after the first 501 patients may be performed.

Substudy 2 - Primary outcome - Learning curve (surgical time)

To evaluate the learning curve associated with robotic-assisted surgery, we will model operative time as a function of case number. Operative time is expected to decrease with experience, then plateau. We will use mixed-effects piece-wise linear regression with the surgeon as a random effect to estimate the case number at which operative time levels off. We will look both at wheel-in wheel-out time (primary), and skin-to-skin time (secondary). We expect to do this analysis after each center has performed 100 robot-assisted spine surgeries, in total 300 surgeries.

We have not conducted a traditional power analysis for this substudy, as the objective is not to test a binary hypothesis but to estimate when operative time stabilizes. If no clear inflection point is observed, this will be interpreted as evidence that the learning curve is either very short (already completed), very gradual, or inconsistent. Such a result would itself be informative, and will require us to compare operative times with today's standard of care, navigated or free hand surgery.

Substudy 3- Primary outcome – Reoperation rate at 2 years

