The primary outcome is the occurrence of reoperations of any cause within 2 years from the index surgery. The expected reoperation rate in the non-robotic group is likely to be higher than 3-5% over a 2-year period [9–11], and may in the robotic-assisted group be 1% or less [12]. A difference of 2 percentage points or greater is considered clinically meaningful. Power analyses (80% power, α 0.05) have been made in two scenarios, with reoperation rates of 3% vs 1%, or 5% vs 3%. We estimate a ratio of 1:6 for robotic-assisted surgery vs navigation-assisted or free hand surgeries.

Comparing 3% and 1% reoperation rates, 420 robotic-assisted surgery patients and 2,520 non-robotic surgery patients are needed (yielding a total sample size of 2,940 patients). In case reoperation rates are 5% and 3%, 866 robotic-assisted surgery patients and 5,196 non-robotic surgery patients are needed (yielding a total sample size of 6,062 patients). An increased proportion of robotic-assisted surgeries or a larger difference in reoperation rates will decrease the total sample size.

An estimated 1800 patients per year are treated with pedicle screw instrumentation at the hospitals, totaling 7,200 patients in 4 years. If we after 4 years deem that the sample size will not be reached in a reasonable time frame, the study will be stopped.

No patients will be lost to follow-up, as outcomes will be ascertained through linkage with national quality, health and surgical registries, requiring no active participation from patients or clinical teams beyond standard registration. If a patient moves abroad before the 2-year period has come to an end, their existing data will be used.

To reduce confounding by indication in this non-randomized design, we will apply both propensity score matching (PSM) and inverse probability weighting (IPW). The propensity score will be estimated using logistic regression, incorporating relevant baseline covariates including age, sex, BMI, smoking status, diagnosis, number of levels fused, revision status, surgical approach (minimally invasive vs. open), interbody device use, and fixed effects for hospital site.

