In the primary analysis, 1:2 nearest-neighbor matching without replacement will be used, with a caliper of 0.2 standard deviations of the logit of the propensity score. Covariate balance after matching will be evaluated using standardized mean differences (SMDs), with $SMD < 0.1$ considered acceptable. Outcome analysis will be performed using Cox proportional hazards regression with robust standard errors to account for matched pairs.

As a secondary analysis, IPW will be used to create a pseudo-population in which treatment assignment is independent of observed covariates. Stabilized weights will be applied, and outcome analysis will be conducted using weighted regression models, adjusted for baseline covariates to enhance robustness.

Although both methods are suitable for dealing with moderate imbalances in group size, it is important to note that reducing the size of the non-robotic group may limit the number of matches available during PSM and could increase variance in the IPW analysis if extreme weights arise. These risks will be mitigated through careful diagnostics, including evaluation of match yield, standardized mean differences, and weight distributions. Overlap weighting or trimming will be considered if weight instability is detected.

While the study is powered at 80% based on the reduced cohort, adjusted analyses using propensity score methods may yield a slightly reduced effective sample size due to matching inefficiency or variance inflation. However, both approaches are expected to preserve sufficient power to detect the prespecified effect size, given the projected event rate and available sample size.

Multiple imputation will be used to handle missing baseline data, and all patients will be included in the final analysis. An increased proportion of robotic surgeries relative to non-robotic surgeries will decrease the overall sample size requirement to detect the same effect.

Secondary outcome - Screw placement precision

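### Substudy 3 is sized for 80% power with six controls per robotic patient, but its primary 1:2 matched analysis has about 70% at the stated sizes, before match losses

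*Protocol*

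**What the plan says.** All the relevant text is in Protocol Section 14, under Substudy 3.

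- Allocation for the power calculation: "We estimate a ratio of 1:6 for robotic-assisted surgery vs navigation-assisted or free hand surgeries".
- Sizes at 80% power and alpha 0.05: for 3% vs 1%, "420 robotic-assisted surgery patients and 2,520 non-robotic surgery patients are needed". For 5% vs 3%, 866 robotic and 5,196 non-robotic.
- Accrual: about 1,800 patients a year, 7,200 over four years. The study stops if, after four years, the sample size is judged out of reach in a reasonable time.
- Primary analysis: "In the primary analysis, 1:2 nearest-neighbor matching without replacement will be used". Matches must lie within 0.2 standard deviations on the logit propensity-score scale, and the outcome model is a Cox regression with robust standard errors. Inverse probability weighting of the whole cohort is secondary.
- On the loss from matching: the protocol ties its 80% to a reduced cohort, describes the fall in effective sample size as slight, and concludes that "both approaches are expected to preserve sufficient power to detect the prespecified effect size". No calculation for a reduced cohort is shown.

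**The concern.** The power calculation and the primary analysis use different data sets. The calculation counts six controls per robotic patient. The analysis keeps at most two, so at least two thirds of the counted controls are set aside by design, however well the matching works. That is a planned change of allocation ratio, and the caliper can only reduce the matched set further.

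This is the primary outcome of what the study timeline (Figure 2) calls the main study. The stated sizes also carry weight in the decision whether to continue after four years. If they are too small for the planned analysis, the target could be declared met too early, and a non-significant result could be credited with more power than it had.

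**Working it through.** **Inputs.** Rates 3% vs 1% (scenario A) and 5% vs 3% (scenario B), alpha 0.05, power 80%, ratio 1:6, sizes 420 and 866 robotic, accrual 7,200: Section 14, Substudy 3. Sidedness is not stated for Substudy 3. I assume two-sided, as in Substudy 1 ("Using a two-sided alpha of 0.05, 80% power, and a 1:6 group ratio"), and this reproduces the figures. Match yields of 90% and 80% are my assumptions.

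**Step 1: reproduce the stated sizes.** Arcsine formula, with k controls per robotic patient:

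h = 2·asin(√p_control) − 2·asin(√p_robotic)
n_robotic = (1.960 + 0.8416)² × (1 + 1/k) / h²

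- A: h = 0.14783, h² = 0.021854. At k = 6: 7.849 × 1.1667 / 0.021854 = 419.0 (stated 420).
- B: h = 0.10286, h² = 0.010580. At k = 6: 7.849 × 1.1667 / 0.010580 = 865.5 (stated 866).

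Other common formulas do not reproduce them: the pooled-variance formula gives 498 and 933, the unpooled formula 289 and 726. So the printed sizes are unmatched 1:6 sizes.

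**Step 2: controls the primary analysis can use.**

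- A: 2 × 420 = 840 of 2,520.
- B: 2 × 866 = 1,732 of 5,196.

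Each is one third of the controls counted for power.

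**Step 3: power at 1:2, same formula.** Power = Φ(h × √(n / (1 + 1/k)) − 1.960), with k = 2.

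| Robotic patients matched | A: 3% vs 1% | B: 5% vs 3% |
|---|---|---|
| All of the stated size (420 / 866) | Φ(2.474 − 1.960) = 69.6% | Φ(2.472 − 1.960) = 69.6% |
| 90% (assumed) | 65% | 65% |
| 80% (assumed) | 60% | 60% |

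**Step 4: robotic patients needed for 80% at 1:2, all matched.**

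- A: 7.849 × 1.5 / 0.021854 = 538.7, so about 539 with 1,078 controls.
- B: 7.849 × 1.5 / 0.010580 = 1,112.8, so about 1,113 with 2,226 controls.

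**Step 5: projected accrual.** 7,200 / 7 = about 1,029 robotic patients at 1:6. With full 1:2 matching:

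- A: Φ(3.871 − 1.960) = 97%.
- B: Φ(2.694 − 1.960) = 77%. At an assumed 90% yield (926 matched): Φ(2.555 − 1.960) = 72%.

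The 539 of step 4 fits within projected accrual. The 1,113 does not.

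**Step 6: dependence on the test.** Power at the stated sizes, 1:2, full matching:

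| Method | A | B |
|---|---|---|
| Arcsine (reproduces the protocol) | 69.6% | 69.6% |
| Pooled two-proportion | 61.9% | 66.8% |
| Unpooled two-proportion | 74.6% | 72.6% |
| Schoenfeld (log-rank/Cox approximation) | 80.9% | 74.1% |
| Simulated score test | 65% | 67% |
| Simulated Wald test, log hazard scale | 59% | 67% |

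In A the robotic arm expects only 420 × 1% = 4.2 events. The Schoenfeld approximation is unreliable there, as the simulated Wald figure of 59% shows. The simulations treat the arms as independent and ignore any precision gained from correlation within matched sets.

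**The case against.** **The stated sizes are minimums.** The protocol rests its power claim partly on the available sample, and 7,200 projected patients are well above 2,940. This stands in part. At full accrual scenario A is well powered at 1:2, and scenario B is about three points short before match losses. But the protocol does not fix which size triggers the analysis, so both cases need to be shown.

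**The loss is disclosed.** The protocol does acknowledge matching inefficiency and plans match-yield diagnostics. It gives no figure, though, and a fall from 80% to about 70% is not slight.

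**The result depends on the formula.** This is true, and Schoenfeld gives 81% in scenario A. With about four robotic events that does not rescue the claim, and in scenario B no method tried reaches 80%.

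**Stronger readings that the documents do not support.**

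- A reader might see a contradiction between matching and the statement that every patient enters the final analysis. That statement shares a sentence with multiple imputation and reads naturally as saying that nobody is dropped for missing baseline data.
- A reader might take "The expected reoperation rate in the non-robotic group is likely to be higher than 3-5% over a 2-year period" to mean that power is lower still. That follows only if the difference is held at 2 points while both rates rise. The protocol pairs this expectation with a robotic rate of 1% or less, so the difference would grow: at 5% vs 1%, 420 + 840 has about 99% power by the arcsine formula. Higher control rates belong in a sensitivity table only.
- A reader might infer that weighting or a wider match would restore 80%. This is not shown. Hospital is in the propensity score, and robots are at two sites with a third pending (Section 15), so controls at other hospitals would carry almost no weight. Matching at 1:6 from a 1:6 pool would use every control and select nothing.

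**Conclusion.** The concern holds as a mismatch between the basis of the power calculation and the primary analysis. The 1:6 arithmetic itself is sound. At the stated sizes, the primary 1:2 matched analysis has about 70% power in both scenarios by the protocol's own formula, and less if the caliper leaves robotic patients unmatched. The claim of 80% is therefore not supported for that analysis at those sizes.

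This does not mean that the study must end underpowered. That depends on accrual and on the true rates: at the projected 7,200 patients, 3% vs 1% is comfortably covered, while 5% vs 3% remains below 80%. The figures assume a two-sided test, the protocol's rates, no loss to follow-up (as the protocol states) and, except where a yield is given, complete matching.

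**What to change.** 1. Calculate and state power for the 1:2 matched cohort under the planned Cox analysis, at both the stated sizes and the projected accrual, for both scenarios.
2. Include an explicit allowance for match yield, and state the number of robotic patients that must be matched. By the arcsine formula this is about 539 (3% vs 1%) or 1,113 (5% vs 3%).
3. Replace three statements in Section 14 with those figures: that 80% power rests on the reduced cohort, that the loss is slight, and that sufficient power is preserved.
4. If the sponsor prefers a primary analysis that retains more controls, calculate its power on its own effective sample size, given hospital in the propensity score and robots at only two or three sites.
5. If control rates above 5% are shown, label them as a sensitivity to the 2-point minimum difference.

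The cost is protocol wording and one recalculated table. No new data collection is needed. The stated power becomes less favourable, and for 5% vs 3% the sponsor must either accept less than 80% or plan for more robotic patients than the current projection provides.

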Patients will be included consecutively at each site during the enrollment window which is planned to be four years (2025–2029). Currently robotic-assisted spine surgery is available in two hospitals (Umeå and Örebro), with a third hospital waiting for their equipment to be installed (Uppsala). If other hospitals install robotic-assisted surgery during the study period this will just result in more patients involved in the robotic-assisted arm of the trial, which would result in a potentially faster inclusion of the needed amount of patients. We still believe that during the study period more patients will be operated with non-robotic-assisted methods than with robotic-assisted methods.

16–17. Allocation and blinding

No randomization or blinding will be performed. If a planned robotic-assisted surgery is abandoned after the start of surgery, the patient will be included in the robotic-assisted group (i.e. intention to treat principle).

18. Data collection methods

Data will be collected through national registries (Swespine, the Swedish Fracture Register, the Swedish PeriOperative Register, hospital systems (electronic health records, surgical planning software, Picture Archiving and Communication System; PACS and others). PROMs will be recorded preoperatively, and at follow-ups (Swespine: 1, 2 and 5 years; the Swedish Fracture Register: 1 year). Images will be retrieved using standardized CT protocols and assessment will be made by at least two researchers independently.

19. Data management

Data will be collected and managed in compliance with GDPR. Regular validation and updates will occur every 6–12 months. Final datasets will be stored at Uppsala University for a minimum of 15 years.

20. Statistical methods

Statistical analysis will compare outcomes using appropriate parametric or non-parametric tests,

including survival methods. Baseline characteristics will be adjusted for using multivariable models. Adjustment variables include age, diagnosis, comorbidities, previous spine surgery, number of levels, number of screws, robotic system type, use of navigation or free-hand surgery and hospital.

Analysis is currently planned to be performed in R. Interim analyses will be performed when half of the patients have been included. Sensitivity analyses will be performed as described earlier.

21. Data monitoring

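### The stabilized-weight analysis of reoperations cannot balance hospital, because only two or three hospitals have a robot, and its target population is not that of the primary matching

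*Protocol*

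**What the plan says.** Everything here concerns substudy 3 in Protocol section 14, unless another section is named.

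- **Primary analysis:** "1:2 nearest-neighbor matching without replacement will be used, with a caliper of 0.2 standard deviations of the logit of the propensity score", followed by Cox regression.
- **Secondary analysis:** "As a secondary analysis, IPW will be used to create a pseudo-population in which treatment assignment is independent of observed covariates". The weights are specified: "Stabilized weights will be applied, and outcome analysis will be conducted using weighted regression models", with further adjustment for baseline covariates that are not listed at that point.
- **Propensity model:** logistic regression on patient and surgical covariates, with fixed effects for hospital site.
- **Hospitals:** section 9 includes every Swedish hospital that performs spinal surgery. Section 15 says that two currently have robotic assistance, a third awaits installation, and others may follow.
- **Safeguards:** the protocol notes that a smaller non-robotic group "could increase variance in the IPW analysis if extreme weights arise". It plans to look at match yield, standardized mean differences and weight distributions, and adds: "Overlap weighting or trimming will be considered if weight instability is detected".

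No target population is named for either analysis.

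**The concern.** Two things go wrong together.

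First, the analyses answer different questions. Matching to robotic patients asks what the robot does for patients who get it and have comparable controls. Stabilized weights ask what would happen if the whole cohort were treated one way or the other. Stabilizing only rescales the weights within each arm, so the target stays the whole cohort.

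Second, this design cannot support the whole-cohort question. At a hospital without a robot nobody can be in the robotic arm, so there is no robotic patient to weight up. The patients there nevertheless remain in the weighted control arm. Any difference in reoperation risk between hospitals with and without a robot, whether from case mix, referral or reoperation practice, then enters the weighted comparison as if it were an effect of the robot.

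The weighted analysis is the only other treatment-effect analysis specified for the main endpoint of a non-randomized study, so readers will set it beside the matched result. If the two disagree, they cannot tell whether the cause is residual confounding in the matching, bias from hospitals without a robot, or a different population.

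**Working it through.** **Inputs from the protocol.** Ratio 1:6, so the robotic share is 1/7. Sample sizes 420 and 2,520 (3% vs 1%) or 866 and 5,196 (5% vs 3%). A difference of 2 percentage points or more is clinically meaningful. Two hospitals have a robot and a third is pending, among all Swedish spine hospitals.

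**Not in the protocol, so assumed.** The cohort share q of hospitals without a robot, the difference in risk between the two kinds of hospital, and the spread of the propensity score.

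**1. The plan's own figures.** With the arcsine formula, two-sided 0.05 and 80% power, n(robotic) = (1.960 + 0.842)² × (1 + 1/6) / h², where h = 2·arcsin√p₁ − 2·arcsin√p₂. For 3% vs 1%, h = 0.1478, giving 420. For 5% vs 3%, h = 0.1029, giving 866. Both reproduce.

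**2. What stabilized weights do to hospital.** Take hospital as the only covariate. At robot hospitals e = (1/7)/(1 − q); elsewhere e = 0. The weights are (1/7)/e for robotic patients and (6/7)/(1 − e) for the others.

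- Weighted controls at robot hospitals, per cohort patient: (1 − q)(1 − e) × (6/7)/(1 − e) = (1 − q) × 6/7.
- Weighted controls elsewhere: q × 6/7, each patient carrying a weight of 6/7 = 0.86.
- Share of weighted controls from hospitals without a robot: exactly q.
- Share of the weighted robotic arm from those hospitals: 0.

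Hospital is therefore unbalanced by the full amount q, however well the propensity model fits.

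**3. Resulting bias when the robot has no effect.** Let reoperation risk be 3% at robot hospitals and 5% elsewhere. The weighted robotic risk is 3%. The weighted control risk is 3% + q × 2 points.

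| q (assumed) | e at robot hospitals | Weighted control risk | False difference, stabilized | False difference, e/(1 − e) weights |
|---|---|---|---|---|
| 0.5 | 0.29 | 4.0% | 1.0 points | 0 |
| 0.7 | 0.48 | 4.4% | 1.4 points | 0 |

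In general the bias is q times the risk difference between the two kinds of hospital, and its sign follows that difference. Weights of e/(1 − e) are zero where e = 0, so they remove those patients and the bias with them.

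**4. Different targets even with full overlap.** Assume a constant risk ratio of 1/3, mean baseline risk 3%, a normal propensity score with slope 1 on the logit scale, and baseline risk with slope −0.5, 0 or +0.5 on the same score. The whole-cohort risk difference is 2.0 points in all three cases. In robotic patients it is 1.4, 2.0 or 2.8 points. The targets agree only when risk is unrelated to selection.

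**5. Precision.** Assume a normal logit propensity with mean 1/7 and full overlap. Variance is taken as 1/ESS(robotic) + 1/ESS(control) from 420 and 2,520, where ESS = (Σw)²/Σw².

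| Logit SD | ESS robotic, stabilized | ESS control, stabilized | ESS control, e/(1 − e) | Variance, stabilized | Variance, e/(1 − e) | Ratio |
|---|---|---|---|---|---|---|
| 0.2 | 97% | 100% | 96% | 0.00285 | 0.00279 | 1.02 |
| 0.5 | 83% | 99% | 79% | 0.00326 | 0.00289 | 1.13 |
| 0.8 | 62% | 98% | 56% | 0.00422 | 0.00309 | 1.36 |
| 1.2 | 35% | 96% | 31% | 0.00729 | 0.00366 | 1.99 |

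Under e/(1 − e) weights the robotic ESS is 100% throughout. For comparison, 1:2 matching at full yield has 1/420 + 1/840 = 0.00357.

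**The case against.** **It is a secondary analysis, and a whole-cohort effect is a legitimate question.** Both are true. The protocol does not call the weighted analysis a check on the matching, and section 20 says only "Sensitivity analyses will be performed as described earlier" without naming it. Agreement between the two would still be informative. But the question has to be answerable from the data, and for hospitals without a robot it is not.

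**The protocol already handles bad weights.** It names the variance risk and a fallback, and an exact trimming limit can be left to the SAP. That stands. The fallback, however, is triggered by unstable weights, and a weight of 0.86 is not unstable. Standardized mean differences would show the problem if hospital were checked after weighting, but the protocol sets its balance criterion only for the matched sample. Overlap weighting or trimming would also bring in another target population.

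**The weighted regression is itself adjusted.** If hospital is among the covariates, as the list in section 20 suggests, the outcome model could absorb most of the bias, provided that the effect does not vary by hospital. This is the strongest reply. The result would then rest on the outcome model rather than on the pseudo-population that the protocol describes, and it would still not be an effect supported at hospitals without a robot.

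**A reader might infer that stabilized weights waste precision because only one patient in seven is robotic.** The documents do not support this. With no propensity spread there is no loss at 1:6. At logit SD 0.5 stabilized weighting is more precise than full-yield 1:2 matching (0.00326 against 0.00357). Any loss depends on a spread that the protocol does not give.

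**Weighting to the robotic population does not match the primary target exactly.** Caliper matching drops robotic patients without a match; e/(1 − e) weights keep them all. This is correct, but the remaining gap is much smaller and can be described.

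**Conclusion.** The point holds for the secondary analysis of substudy 3 and should be corrected. The lack of support at hospitals without a robot follows from the protocol's own statements on participating hospitals, robot availability and the propensity model, and needs no assumed distribution.

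The size of the bias does rest on assumptions. It is 1.0 to 1.4 points if hospitals without a robot hold 50 to 70% of the cohort, their risk is 5% against 3%, and the outcome model does not correct for hospital. It is zero if risk does not differ between the two kinds of hospital, and it shrinks as more hospitals acquire a robot.

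On precision, the most that can be said is that the variance is about 1.0 to 2.0 times that of robotic-population weights for a logit SD of 0.2 to 1.2, under a normal-logit assumption. The protocol's expectation that "both approaches are expected to preserve sufficient power to detect the prespecified effect size" can be neither confirmed nor refuted for the weighted analysis without a propensity distribution.

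A reader might also infer that the primary result is compromised. It is not on this ground: with hospital in the propensity score, patients at hospitals without a robot are largely left unmatched.

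**What to change.** - State the target population of each analysis. For the primary analysis it is robotic patients who can be matched.
- Restrict the weighted analysis to hospitals, and to calendar periods within them, where both methods are in use. The period matters because one hospital is still waiting for its equipment and others may start during the study.
- Replace the stabilized weights by 1 for robotic patients and e/(1 − e) for the others.
- Report covariate balance after weighting with hospital included.
- Label any overlap-weighted or trimmed estimate as having its own target population.

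This takes a sentence or two in the protocol and a line of code. The price is that no effect is estimated for hospitals without a robot, which the data cannot support in any case. Depending on the propensity spread, precision should be similar to or better than that of stabilized weights applied to the same patients.

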We will evaluate screw placement precision as the deviation between preoperative planning and actual placement in robotic-assisted surgery cases. For each screw, linear deviation (at the tip and tail) perpendicular from the planned position, to the actual position, and angular deviation between the planned position and the actual position will be measured. This comparison will be made on an overlay of the preoperative planning made on a preoperative computed tomography, and compared with the computed tomography performed intra- or postoperative for assessment of pedicle screw position.

Stratified comparisons (e.g., by spinal level or surgeon experience) may be performed to identify patterns of deviation. We plan to use the first 60 cases in the study in each of 3 centers that perform robotic-assisted spine surgery for this analysis, and for comparison divide them into a first ($n=30*3$) and second group ($n=30*3$), in all 180 cases.

Other secondary outcomes

Other complications

Thromboembolic, cardiovascular complications and mortality will be assessed as secondary safety outcomes. These events are rare in spine surgery, and although the study is not powered to detect small differences in such outcomes, comparisons between robotic and non-robotic cohorts will be reported.

Other outcomes

Length of stay, time to return to work will be described, but no power calculation has been made.

Health economic analysis

A health economic analysis will be performed and resource use described. No power calculation has been made.

Patient reported outcomes (PROMs)

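### Splitting robotic case order into first 30 and second 30 per centre for screw precision discards information that a trend over case number would keep, if deviation declines gradually

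*Protocol*

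**What the plan says.** Section 14 of the protocol, under the secondary outcome of screw placement precision, defines the measure: "We will evaluate screw placement precision as the deviation between preoperative planning and actual placement in robotic-assisted surgery cases". Linear deviation (tip and tail) and angular deviation are measured for each screw.

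The sample is given next: "We plan to use the first 60 cases in the study in each of 3 centers that perform robotic-assisted spine surgery for this analysis". The one comparison that is laid out is to "for comparison divide them into a first ($n=30*3$) and second group ($n=30*3$), in all 180 cases". A further option is left open: "Stratified comparisons (e.g., by spinal level or surgeon experience) may be performed to identify patterns of deviation". No test, standard deviation, target difference or power is given for precision.

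In the same section, Substudy 2 treats experience differently. Operative time is modelled against case number by "mixed-effects piece-wise linear regression with the surgeon as a random effect", and the expected shape is stated: "Operative time is expected to decrease with experience, then plateau". That expectation is for operative time. No curve is stated for precision.

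**The concern.** The split gives case 1 and case 30 the same experience and treats cases 30 and 31 as different. The protocol gives no reason for cutting at 30. If deviation improves early and then settles, the first block mixes early cases with cases that have already settled, and the difference between the two blocks shrinks.

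Two things are at stake. A real improvement in precision is more likely to be missed than it need be. And a difference between two means at a fixed cut says nothing about when precision stabilises, so it cannot be set beside the Substudy 2 estimate of when operative time levels off, although the two analyses draw on largely overlapping early robotic cases (60 and 100 per centre).

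**Working it through.** **Stated figures.** The only figure for this comparison is the count: 2 × 30 × 3 = 180, which adds up. There is no power figure to reproduce.

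**Inputs from the protocol.** 60 cases in each of 3 centres, cut at case 30, with a continuous outcome.

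**Assumptions.**
- Two-sided alpha of 0.05, with 80% as the reference power of the split. The protocol states these values for Substudy 1 ("Using a two-sided alpha of 0.05, 80% power, and a 1:6 group ratio"), not for precision.
- One independent value per case, with equal variance.
- True curve: linear decline to a plateau at case k (k = 5 to 60, where 60 means no plateau), exponential decline, or an abrupt step.

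**Method.** For a one-degree-of-freedom contrast, the noncentrality is proportional to the correlation r between the contrast and the true mean curve over cases 1 to 60. So:

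- information kept by the split = (r_split / r_trend)²
- noncentrality of the split at 80% power = 1.960 + 0.842 = 2.802
- noncentrality of the trend = 2.802 × r_trend / r_split
- power of the trend ≈ Φ(noncentrality − 1.960)

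Example, plateau at case 20: information kept = (0.567 / 0.770)² = 0.54. Trend noncentrality = 2.802 × 0.770 / 0.567 = 3.80, and Φ(3.80 − 1.96) = 96.7%.

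| True curve | r, split | r, trend | Information kept by split | Trend power when split has 80% |
|---|---|---|---|---|
| Plateau at case 5 | 0.243 | 0.399 | 0.37 | 99.6% |
| Plateau at case 10 | 0.367 | 0.568 | 0.42 | 99.1% |
| Plateau at case 20 | 0.567 | 0.770 | 0.54 | 96.7% |
| Plateau at case 30 | 0.764 | 0.890 | 0.74 | 90.4% |
| Plateau at case 40 | 0.873 | 0.960 | 0.83 | 86.8% |
| Steady decline to case 60 | 0.866 | 1.000 | 0.75 | 89.9% |
| Exponential, constant 5 cases | 0.446 | 0.646 | 0.48 | 98.2% |
| Exponential, constant 30 cases | 0.826 | 0.969 | 0.73 | 90.8% |
| Abrupt step after case 30 | 1.000 | 0.866 | 1.33 | 68.0% |

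**Where the split wins.** With an abrupt step, trend power is 78.5% at case 26, 73.5% at case 28, 68.0% at case 30, 73.5% at case 32 and 78.5% at case 34. At cases 25 and 35 it is 80.8%, so the advantage has gone. A steep S-shaped change centred at case 30 also favours the split.

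**Sensitivity to the reference power.** If the trend rather than the split is held at 80%, the split has 44.0% (plateau at case 10), 54.2% (case 20), 67.2% (case 30) and 72.2% (case 40). The gap in percentage points therefore depends on the calibration. The information ratio does not.

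**Simulation check** (20,000 runs, centre effects, mean difference between halves of about 0.42 SD). Split against trend: 79.0% and 86.0% for a plateau at case 40, 78.9% and 89.8% at case 30, 76.3% and 95.8% at case 20. The picture is the same.

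**The case against.** The strongest reply is that the split is offered as a simple description for an unpowered secondary outcome, with no hypothesis attached. Stratification by surgeon experience is allowed, section 20 allows multivariable models, and detailed modelling may be left to an SAP that is not shown. In part this stands: nothing in the protocol is false or contradictory here. But the split is an analysis choice that the protocol makes itself, and neither optional stratification nor a general list of methods restores case order once cases are grouped in two halves.

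Three further limits stand.

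- A reader might infer that the protocol itself expects precision to decline and then plateau, and that the split therefore fails on the plan's own terms. The protocol does not support that. It states the shape for operative time only.
- The power figures are for a linear trend, which cannot locate a plateau. A piece-wise fit with unknown plateau gains less when the plateau is late: in simulation, with the split at about 79% to 80%, it had 84% (plateau at case 40), 82% (case 50) and 83% (case 60). It does better for early plateaus.
- Section 15 says robotic surgery is already available at two hospitals, so study case 1 need not be a centre's first robotic case. For an exponential decline this changes nothing in the comparison, because a later start only rescales the curve. For other shapes it shifts the plateau to an earlier study case.

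**Conclusion.** The point holds as a cheap improvement to a secondary analysis. For every steady, decline-then-plateau or exponential curve examined, the 30/30 split kept less information than a linear trend: about 37% to 83% over plateaus at cases 5 to 60. With the split at an assumed 80% power, the trend has about 87% to just over 99%.

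These figures rest on assumptions outside the protocol: a gradual curve for precision, one independent value per case, and the 80% reference. Several screws per patient and shared surgeons would change absolute power. It would be wrong to read a single fixed loss of power into the plan, or to say that the split is always worse: an abrupt change at about cases 26 to 34 reverses the ranking.

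**What to change.** Make the precision comparison a mixed model of per-screw deviation on continuous robotic case number, with the linear trend as the test, random effects for patient and surgeon, and a centre term. If an estimate of when precision levels off is wanted, add the Substudy 2 piece-wise form as a supporting analysis. Keep first 30 against second 30 as a descriptive table.

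The cost is about one sentence of text and slightly more modelling, with no new patients, imaging or data. The result is a little less simple to read than two group means, and there is less power if precision changes abruptly near case 30.
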